## **9.2 Subject Accountability**

The number and percent of subjects who were screened, enrolled, received at least one dose of AMG 673, completed investigational product, discontinued from investigational product (including reasons for discontinuing), completed study, discontinued the study (including reasons for discontinuing) will be summarized overall and by dose cohort.

Key study dates for the first subject enrolled, last subject enrolled, and last subject's end of study will be presented. A subject listing and summary noting inclusion in each analysis subset will be provided for all subjects enrolled. A subject listing noting, reason for discontinuation of treatment, and reason for discontinuing the study will be provided. A list of subjects screened but not enrolled (screen failures) will be provided.

## **9.3 Important Protocol Deviations**

Important Protocol Deviations (IPDs) categories are defined by the study team before the first subject's initial visit and updated during the IPD reviews throughout the study prior to database lock. These definitions of IPD categories, subcategory codes, and descriptions will be used during the course of the study. Eligibility deviations are defined in the protocol.

## **9.4 Demographic and Baseline Characteristics**

Demographic (ie, age, age groups [18-64, 65-74, 75-84 and  $\geq$  85], sex, race, ethnicity) and baseline characteristics will be summarized by dose cohort and overall using descriptive statistics. If multiple races have been reported for a subject, the subject will be categorized as multiple race as well as by the combination of race.

## **9.5 Efficacy Analyses**

Not Applicable

### **9.5.1 Analyses of Primary Efficacy Endpoint(s)**

Not Applicable

### **9.5.2 Analyses of Secondary Efficacy Endpoint(s)**

Listings will be produced for all subjects in the dose-escalation cohorts and the dose-expansion cohorts indicating the time to progression, time to response, and duration of response Event free Survival . The proportion of subjects with a CR/CRh\*/CRi/morphologic leukemia-free state with corresponding exact 80% CI will be calculated using the Clopper-Pearson method (Clopper and Pearson, 1934) and tabulated for subjects treated at the MTD/**RP2D**. Kaplan Meier curve may be presented for time to progression with estimates for rates and 80% CI at selected weeks. Statistical analyses of efficacy endpoints will be considered exploratory.

### **9.5.3 Analyses of Exploratory Efficacy Endpoint(s)**

Not Applicable

## **9.6 Safety Analyses**

### **9.6.1 Analyses of Primary Safety Endpoint(s)**

Unless otherwise specified, statistical analyses on safety endpoints will be done using subjects from the safety analysis set, which includes subjects that are enrolled and received at least 1 dose of AMG 673.

Subject incidence of DLTs will be used to fit the BLRM model to estimate the probability of having a DLT across dose levels.

### **9.6.2 Adverse Events**

The Medical Dictionary for Regulatory Activities (MedDRA) version 19.0 or later will be used to code all events categorized as adverse events to a system organ class and a preferred term.

The severity of each adverse event will be graded using CTCAE version 4.0 criteria.

The severity of each CRS event will be graded according to the guidelines provided in Table 5 [based on the adopted grading system referenced in Lee et al (Blood 2014)] in the protocol.

Treatment-emergent adverse events are events with an onset after the administration of the first dose of investigational product.

Subject incidence of all treatment-emergent adverse events will be tabulated by system organ class and preferred term. The number and percentage of subjects reporting adverse events will be evaluated overall and by dose level and will also be tabulated by relationship to study drug.

Tables of disease-related events, fatal adverse events, serious adverse events, adverse events leading to withdrawal from investigational product or other protocol-required therapies, and significant treatment-emergent adverse events will also be provided.

Subject incidence of all disease-related events, fatal disease-related events, serious disease-related events, disease-related events leading to withdrawal from investigational product or other protocol-required therapies, and significant disease related events will also be provided. Subject incidence of disease-related events and fatal disease-related events will be tabulated by system organ class and preferred term. Subject incidence of first dose effects will be used to fit the BLRM model to estimate the probability of having an adverse event related to first dose effects across dose levels.

### **9.6.3 Laboratory Test Results**

Clinical chemistry, hematology, and urinalysis data will be listed and reviewed for each subject. Values outside the normal laboratory reference ranges will be flagged as high or low on the listings.

Additionally, the number and percentage of subjects experiencing 0,1, 2, 3 and 4 worsening CTCAE grade shifts from baseline will be presented. The direction of the laboratory worsening will again be denoted.

Shifts tables indicating the change between the baseline and the maximum post dose CTCAE grades for an increased value, and the maximum post dose grade for a decreased value will be provided for selected laboratory parameters of interest.

Summaries of the absolute value and/or changes from baseline at each scheduled assessment will be provided for selected laboratory parameters of interest.

A summary of the change from baseline to the post dose maximum, time to post-dose maximum, change from baseline to the post dose minimum, and the time to the post dose minimum may also be provided for selected parameters of interest.

Below is list of all lab tests performed:

Local Laboratory					Central Laboratory
Chemistry	Hematology	Urinalysis	Coagulation	Other Labs	
Sodium	Erythrocytes	Specific gravity	PT	Pregnancy test a	
Potassium	Hemoglobin	pH	PTT	Serology (HepB, HepC)	Pharmacokinetics
Bicarbonate	Hematocrit	Blood Protein	INR	Bone marrow cytology and cytochemistry	Cytokines
Or	MCV	Glucose	Fibrinogen	Standard bone marrow	Blood
Total CO 2	Platelets	Bilirubin	AT III		
Chloride	WBC Differential	Ketones			
Total protein	Total Neutrophils	Microscopic exam			
Albumin	Seg. Neutrophils	(performed at the discretion of the investigator)			
Calcium	Lymphocytes				
Magnesium	Atypical Lymphocytes				
Phosphorus	Monocytes				
Glucose	Bands/Stabs				
BUN	Eosinophils				
Urea	Basophils				
Creatinine	Blasts				
Total bilirubin	Myeloblasts				
ALP	Monoblasts				
AST	Megakaryoblasts				
ALT	Promyelocytes				
Amylase	Myelocytes				
Lipase	Metamyelocytes				
CRP	Nucleated RBC				
LDH	Immature Granulocytes				
Uric Acid					
Ferritin					

ALP = alkaline phosphatase; ALT = alanine aminotransferase; anti-HBc = Hepatitis B core antibody; AST = aspartate aminotransferase; AT III = Antithrombin III; CRP = C-reactive protein; HepBsAg = hepatitis B surface antigen; HepCAb = hepatitis C antibody; INR = international normalize ratio; LDH = lactate dehydrogenase; MCV = mean corpuscular volume; MRD = Minimal Residual Disease; PT = prothrombin time; PTT = partial thromboplastin time; WBC = white blood cell

a Serum pregnancy test will be performed for all females unless surgically sterile or ≥ 2 years postmenopausal.

#### 9.6.4 Vital Signs

Vital signs data will be listed and reviewed for each subject. Depending on the size and scope of changes, summaries of vital signs data over time and/or changes from baseline over time may be provided.

#### 9.6.5 Physical Measurements

The change in weight from baseline to each scheduled assessment time point will be summarized.

### 9.6.6 Electrocardiogram

All on-study electrocardiogram (ECG) data will be listed and select parameters of interest may be plotted.

Summaries over time and/or changes from baseline over time will be provided for all ECG parameters.

The analysis of Fridericia's (QTcF) QT correction will use the results recorded on the CRF. Subjects' maximum change from baseline in QT interval corrected by Fridericia's formula will be categorized into the following groups per their maximum change from baseline in QTcF. Unscheduled assessments will be included in the determination of the maximum change.

[figure not shown]
- $\leq 30$  msec
- $>30 - 60$  msec
- $>60$  msec

The number and percentage of subjects in each group will be summarized.

Subjects will also be categorized into the following groups per their maximum post baseline QTcF. Unscheduled assessments will be included in the determination of the maximum post baseline value.

- $\leq 450$  msec
- $>450 - 480$  msec
- $>480 - 500$  msec
- $>500$  msec

The number of subjects in each group will be summarized for each dosing group.

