2.2.3 Nonclinical Toxicology

The nonclinical safety assessment of AMG 673 consisted of a 28-day intravenous (IV) toxicology study in monkeys. The monkey was selected as the toxicology species based on target binding affinity and bioactivity data. The intravenous route of administration was chosen based on the intended clinical route of administration. The results of the 28-day monkey toxicology study with AMG 673 were consistent with its expected pharmacology, ie, cytotoxic T-cell redirected lysis of CD33-expressing bone marrow cells and leukocytes, and included increased cytokines, decreased circulating leukocytes, red cell mass and platelets, changes in clinical chemistry parameters suggestive of an acute phase response, and increased heart rate. All of these changes exhibited full or partial reversibility. One animal from the high-dose group (30 μ g/kg) had decreased activity approximately 4.5 hours after administration of the first dose and was euthanized soon thereafter due to poor clinical condition; the morbidity in this animal was attributed to complications from cytokine release. All other animals survived to scheduled termination; there were no AMG 673-related light microscopic changes in these animals. All surviving animals developed antidrug antibodies (ADA) that were associated with complete or nearly complete loss of exposure by day 14. Despite the loss of exposure, the study is valid to support the proposed clinical trial because all of the AMG 673-related changes were as expected for a CD33-directed activator of T-cells. Based on the unscheduled euthanasia at 30 μ g/kg, the highest non-severely toxic dose (HNSTD) was determined to be 15 μ g/kg.

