7.3.8 Electrocardiogram Performed in Triplicate

The subject must be in supine position in a rested and calm state for at least 5 minutes before ECG assessment is conducted. If the subject is unable to be in the supine position, the subject should be in most recumbent position as possible.

Electrocardiograms should be performed in a standardized method, in triplicate, and approximately 30 seconds apart, prior to blood draws or other invasive procedures. Each ECG must include the following measurements: QRS, QT, QTc, RR, and PR intervals.

Electrocardiograms will be performed as follows:

- Three sets of baseline ECGs will be collected ≥ 30 minutes apart, with each baseline ECG in triplicate run consecutively (ie, < 30 seconds apart; 2 sets collected at screening, and 1 set collected pre-dose on day 1 [ie, total ≥ 9 ECGs])
- Triplicate ECGs at time points after dosing

Baseline is defined as predose assessments from cycle 1 day 1. The investigator or designated site physician will review all ECGs. Electrocardiograms will be transferred electronically to an ECG central reader for analysis per Amgen instructions. Once signed, the original ECG tracing will be retained with the subject's source documents. At the request of the sponsor, a copy of the original ECG will be made available to Amgen.

Standard ECG machines should be used for all study-related ECG requirements.

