Subjects' maximum change from baseline in QT interval corrected by Fridericia's formula will be categorized and the number and percentage of subjects in each group will be summarized.

Subjects' maximum post baseline values will also be categorized and the number and percentage of subjects in each group will be summarized.

All on-study ECG data will be listed, and select parameters of interest may be plotted.

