## List of Abbreviations

Abbreviation	Explanation
AUC	Area under concentration time curve
C max	maximum observed concentration
CRF	case report form
CRS	Cytokine Release Syndrome
DLRM	dose level review meeting
DLT	dose limiting toxicity
ECG	Electrocardiogram
eCRF	electronic case report form
end of study for individual subject	defined as the last date that protocol-specified procedures are conducted for an individual subject
end of treatment	defined as the date of final assessment for the protocol specified treatment phase of the study for an individual subject
end of study (primary completion)	defined as the date when the last subject is assessed or receives an intervention for the purposes of final collection of data for the primary endpoint(s).
Ig	Immunoglobulin
ICF	informed consent form
IP	Investigational Product
PD	pharmacodynamic
PK	pharmacokinetic
PR	the interval measured from the beginning of the P wave to the beginning of the QRS complex in the heart's electrical cycle as measured by electrocardiogram
QRS	the interval between the Q wave and the S wave in the heart's electrical cycle as measured by electrocardiogram; represents the time it takes for depolarization of the ventricles
QT	measure of the time between the start of the Q wave and the end of the T wave in the heart's electrical cycle as measured by electrocardiogram
QTc	QT interval corrected for heart rate using accepted methodology
study day 1	defined as the first day that protocol specified investigational product is administered to the subject
t max	time to maximum concentration

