### Bazett-corrected QT Interval (QTcB)

The Bazett correction will be calculated from the investigator reported QT (msec) and RR interval (msec), as follows:

$$QTcB = QT / (RR/1000)^{1/2}$$

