### Cmax

Maximum observed serum concentration.

Cmin

Minimum observed serum concentration

End-of-Study

Primary Completion: The primary completion date is defined as the date when the last subject is assessed or receives an intervention for the purposes of final collection of data for the primary endpoint(s), for the purposes of conducting the primary analysis, whether the study concluded as planned in the protocol or was terminated early.

The primary completion date is the date when the last subject either had the opportunity to receive up to 2 cycles of treatment or terminated the study early.

If the study concludes prior to the primary completion date originally planned in the protocol (ie, early termination of the study), then the primary completion will be the date when the last subject is assessed or receives an intervention for evaluation in the study (ie, last subject last visit).

End of Study: The end of study date is defined as the date when the last subject is assessed or receives an intervention for evaluation in the study (ie, last subject last visit); the final analysis will occur at this time.

Enrollment Date

Enrollment date is defined as the first dose of IP date.

Fridericia-corrected QT Interval (QTcF)

The Fridericia correction will be calculated from the investigator reported QT (msec) and RR interval (msec), as follows:

$$QTcF = QT / (RR/1000)^{1/3}$$

Investigational Product

The term 'investigational product' is used in reference to AMG 673.

Percent Change From Baseline

Percent change from Baseline is the arithmetic difference between post-Baseline and Baseline divided by Baseline values times 100.

Percent change from baseline =  $[(\text{Post-baseline Value} - \text{Baseline Value}) / \text{Baseline Value}] \times 100$

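### Does the SAP leave it open which QTcF value goes into the ECG tables?

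*SAP*

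**What the plan says.** SAP Section 5 (Definitions, Fridericia-corrected QT interval) gives a derivation: "The Fridericia correction will be calculated from the investigator reported QT (msec) and RR interval (msec"), with QTcF = QT / (RR/1000)^(1/3). The same section defines a Bazett value separately, under its own label QTcB: "The Bazett correction will be calculated from the investigator reported QT (msec) and RR interval (msec"), with exponent 1/2.

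SAP 9.6.6 (Electrocardiogram) names the source for the Fridericia analysis: ("QTcF) QT correction will use the results recorded on the CRF". It then groups subjects by maximum QTcF change (≤30, >30–60, >60 msec) and by maximum QTcF (cut-offs 450, 480 and 500 msec).

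Protocol 10.4.2 commits to the same correction, referring to each subject's "maximum change from baseline in QT interval corrected by Fridericia"'s formula. Protocol 7.3.8 lists what a tracing has to show: "Each ECG must include the following measurements: QRS, QT, QTc, RR, and PR intervals". It also arranges a central read: "Electrocardiograms will be transferred electronically to an ECG central reader for analysis per Amgen instructions".

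The abbreviation lists leave the QTc formula open. The SAP's entry reads "QT interval corrected for heart rate using accepted methodology".

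**The concern.** One SAP section describes a calculation and another points to recorded results. If those results are QT and RR, the two say the same thing. If they are a corrected value typed in by the site, the formula behind that value matters. Protocol 7.3.8 requires a QTc and names no formula, and the SAP itself recognises two.

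The choice of formula matters most when heart rate moves, and this trial expects that. The monkey study showed "changes in clinical chemistry parameters suggestive of an acute phase response, and increased heart rate", tachycardia is listed as a sign of cytokine release syndrome, and Protocol Table 5 gives 120 bpm as an example of persistent tachycardia. ECGs are scheduled at the end of infusion and at 24 hours. The tables use each subject's maximum and include unscheduled tracings. If a Bazett value were tabulated as QTcF, a faster heart rate alone could move a subject into a higher category. The central read looks like a possible third source, since the visible SAP text does not mention it.

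**Working it through.** The plan states no figure to reproduce here. The check has three steps.

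**1. What the feared error would do.** Dividing the two formulas in SAP Section 5 gives

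QTcB = QTcF × (RR/1000)^(−1/6) = QTcF × (HR/60)^(1/6).

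Assume QTcF is constant at 410 msec; neither document gives a level.

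- At 120 bpm: RR = 500 msec, QT = 410 × 0.5^(1/3) = 325.4 msec, QTcB = 325.4 / 0.5^(1/2) = 460.2 msec.
- At 70 bpm: QT = 389.5 msec, QTcB = 420.7 msec.
- Apparent change by Bazett: 460.2 − 420.7 = +39.5 msec. True Fridericia change: 0.

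Apparent change at 120 bpm from other assumed baselines:

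| Baseline heart rate (bpm) | Apparent change (msec) |
|---|---|
| 60 | +50.2 |
| 80 | +30.1 |
| 90 | +21.5 |

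These shifts would matter if they could arise under the plan.

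**2. Whether the plan allows it.** The figures in step 1 need three things together: a QTc field on the CRF, a site QTc corrected by Bazett, and that value tabulated under the name QTcF.

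- Neither document shows the first. Protocol 7.3.8 says what an ECG must contain, not what is entered on the CRF. The signed tracing stays with the source documents.
- Neither document shows the second. No site method is named.
- The SAP rules out the third. Section 5 defines QTcF by the Fridericia formula and gives Bazett a different name. The sentence in 9.6.6 that mentions the CRF has the Fridericia correction as its subject, and the sentence after it names Fridericia's formula again. Protocol 10.4.2 does the same.

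**3. How far the permitted readings differ.** Two remain: (a) derive QTcF from the QT and RR on the CRF; (b) use a Fridericia value recorded on the CRF. Take QT 360 msec at 100 bpm (RR 600 msec), and assume each recorded number is rounded to the nearest msec.

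- Reading (a): 360 / 0.6^(1/3) = 426.8 msec.
- Rounding of QT contributes at most 0.5 / 0.6^(1/3) = 0.59 msec.
- Rounding of RR contributes at most 426.8 × (1/3) × (0.5/600) = 0.12 msec.
- Rounding of a recorded QTcF contributes at most 0.5 msec.
- Largest gap between (a) and (b): 0.59 + 0.12 + 0.5 = 1.2 msec.

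Only a subject within about that distance of a cut-off could be classed differently.

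On the central read, Section 5 specifies values reported by the investigator and 9.6.6 specifies the CRF. Both indicate the site's data for these tables.

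**The case for a change.** The strongest case for a change is that a programmer working from 9.6.6 alone could pull whatever corrected value the CRF holds. The CRF is not among the documents, so nobody reading them can exclude a QTc field of unknown formula. The repair would be one clause, would need no new data, and would remove any later choice between sources. If the CRF holds only QT and RR, the clause would merely confirm practice.

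Part of this stands. The SAP does leave unstated whether QTcF is derived or taken as recorded, and no visible passage says what the central read is for. Some SAP entries are redacted, so silence on the central read proves little.

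The part that fails is the consequence. An analyst who finds a QTc of unnamed formula cannot label it QTcF without departing from Section 5, which holds the formula and names its inputs. Protocol 7.3.8 requires those inputs, QT and RR, on every ECG. The shifts of +21.5 to +50.2 msec measure a departure from the plan, not a choice that it leaves open.

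**Conclusion.** No change is needed. The correction is fixed as Fridericia in both documents, and the natural reading of the two SAP passages is that Section 5 gives the derivation and 9.6.6 the data source. Readings that follow the plan differ by rounding only, at most about 1.2 msec in the worked example with values recorded to the nearest msec. The larger shifts rest on an assumed QTcF of 410 msec, assumed heart rates, an assumed Bazett value at the site and its use against the SAP's own definition.

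The stakes are also low. The QTcF tables are descriptive, all on-study ECG data are listed, and no QTcF category determines a DLT or enters the Bayesian logistic regression model. The missing source clause is a detail that an analyst fills correctly from Section 5, and writing it down would alter no result or conclusion.
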